7 RISKS AND PROTECTIONS

7.1 Potential Risks to Subjects

Risk to Confidentiality: There is a potential risk to confidentiality due to the protected health

information collected and stored in the subject's research record.

Risk from Blood draw: There may be a minor amount of discomfort due to the phlebotomy. There is a minor risk of bruising (< 1%), infection at the phlebotomy site (< 1%) or dizziness following the blood draw (<1%).

Risk from Information on Cytomegalovirus (CMV) Serology and Infection: Given the frequency of CMV positive titers in the aged population and the potential influence on immune responses to pneumococcal vaccines (6), individual samples will be evaluated in the Jackson Laboratory for Genomic Medicine as to CMV serology and infection.

Risk from Vaccination with Prevnar-13

As stated in Prevnar 13 Prescribing Information the following risks are known to occur after vaccination with Prevnar 13:

- In adults aged 50 years and older the commonly reported solicited adverse reactions were pain at the injection site (>50%), fatigue (>30%), headache (>20%), muscle pain (>20%), joint pain (>10%), decreased appetite (>10%), injection site redness (>10%), injection site swelling (>10%), limitation of arm movement (>10%), chills (>5%) or rash (>5%).
- In adults, antibody responses to Prevnar 13 were diminished when given with inactivated trivalent influenza vaccine (TIV).
- Prevnar 13 does not protect against disease caused by *S. pneumoniae* serotypes that are not in the vaccine.

Risk from Vaccination with Pneumovax-23

As stated in Pneumovax-23 Prescribing Information, risks known to occur from vaccination with Pneumovax-23 are as follows:

- The most common adverse reactions, reported in >10% of subjects vaccinated with Pneumovax 23 in clinical trials, were: injection-site pain/soreness/tenderness (60.0%), injection-site swelling/induration (20.3%), headache (17.6%), injection-site erythema (16.4%), asthenia and fatigue (13.2%), and myalgia (11.9%).
- Pneumovax 23 will not prevent disease caused by capsular types of *S. pneumoniae* other than those contained in the vaccine.
- In a randomized clinical study, a reduced immune response to Zostavax® as measured by ELISA was observed in individuals who received concurrent administration of Pneumovax 23 and Zostavax compared with individuals who received these vaccines 4 weeks apart. Consider administration of the two vaccines separated by at least 4 weeks.

Risks from OPTIONAL second vaccination one year after initial vaccine (Visit 7)

- Risk to participants randomized to Prevnar 13 who opt to receive Pneumovax 23 a year after initial vaccination.
At one year, this sequence is consistent with CDC recommendations for 2015, therefore risk is consistent with that of routine medical care. Data is available only for antibody response to the 12 serotypes that the two vaccines have in common, and for these, the

second vaccination at one year results in similar antibody levels as an initial Prevnar 13 vaccination.

- Risk to participants randomized to Pneumovax 23 who opt to receive Prevnar 13 one year after initial vaccination.

In patients 60-64 years old, antibody response to the 13 serotypes in Prevnar 13 were found to be lower when given a year after Pneumovax 23 than when Prevnar is given as an initial vaccination. There is no available data for antibody response to all 23 serotypes of *S. pneumoniae* in Pneumovax 23 when followed by Prevnar 13.

7.2 Adequacy of Protection Against Risks

This study will be conducted under the supervision of the Principal Investigator, [name]. Best medical practices will be followed during all procedures. UConn Health emergency care procedures will be followed if an adverse event or medical emergency occurs. The study site is located on the campus of a tertiary care hospital that is available for treatment of medical emergencies.

Protection against Risk to Confidentiality:

All study visits will occur in a private room at the UConn Center for Aging at UConn Health in Farmington, CT.

Research records will be labeled with a participant ID number (PID), an assigned unique identifier that is not derived from any patient identifiers. All contents of the research record will be labeled with the assigned PID. Research records will be stored in a secure area. A complete record of the subject's pertinent history and documentation of the clinical visits will be kept on case report forms and will be stored in a secure area. Research records will be accessible only to the study team directly involved in conduct of the clinical protocol.

Any study documents (Informed Consent Form, HIPAA Authorization, Visit 7 Opt-in form) that contain the participant's name will be kept in a separate file apart from the research record and will be stored in a secure location. A master key that links participant names and PIDs will be maintained in a separate and secure location.

The database manager follows the Data Safety and Security Policy and Confidentiality agreement. These Policies provide procedures to assure that volunteer information remains confidential. All persons in the Recruitment Database have been asked to give permission to leave their name in the database. This policy will be included in this study.

The study database is password protected and secure, thus allowing only certain individuals access to the information. In addition, the database can be monitored in order to track the date, time, and individual who entered the database.

Samples/specimens will be labeled with PID, date, and visit number when they are delivered to the Jackson Laboratory for Genomic Medicine (JAX) for processing, storage and analysis.

A coded clinical data set linked to samples by PID will be provided to JAX for use in analysis. Results of this study when published will not identify subjects by name.

Certificate of Confidentiality:

This research is covered by a Certificate of Confidentiality from the National Institutes of Health. The researchers with this Certificate may not disclose or use information, documents, or biospecimens that may identify you in any federal, state, or local civil, criminal, administrative, legislative, or other action, suit, or proceeding, or be used as evidence, for example, if there is a court subpoena, unless you have consented for this use. Information, documents, or biospecimens protected by this Certificate cannot be disclosed to anyone else who is not connected with the research except, if there is a federal, state, or local law that requires disclosure (such as to report child abuse or communicable diseases but not for federal, state, or local civil, criminal, administrative, legislative, or other proceedings, see below); if you have consented to the disclosure, including for your medical treatment; or if it is used for other scientific research, as allowed by federal regulations protecting research subjects.

The Certificate cannot be used to refuse a request for information from personnel of the United States federal or state government agency sponsoring the project that is needed for auditing or program evaluation by NIH National Institute of Allergy and Infectious Diseases (NIAID) which is funding this project. You should understand that a Certificate of Confidentiality does not prevent you from voluntarily releasing information about yourself or your involvement in this research. If you want your research information released to an insurer, medical care provider, or any other person not connected with the research, you must provide consent to allow the researchers to release it.

The Certificate of Confidentiality will not be used to prevent disclosure as required by federal, state, or local law of information about elder, spousal abuse, reportable communicable diseases. The investigators on this study will report this information to State officials if it becomes known to them. The Certificate of Confidentiality will not be used to prevent disclosure for any purpose you have consented to in this informed consent document.

A description of this clinical study will be available on <http://www.ClinicalTrials.gov>. This Website will not include information that can identify participants. At most, the Web site will include a summary of the results. Participants will be informed in the consent that they can search this Website at any time.

Protection against Risk from Blood Draw:

Blood will be drawn peripherally via venipuncture at all visits. The volume drawn will be 50 mL at Visits 1, 3, 4, 5, 6 & (optional visit) 7 and 10 mL at Visit 2. Blood will be drawn by

experienced, trained research staff in a clinic setting on a hospital campus. The area where the needle will be inserted will be wiped with alcohol before and after the draw. A band-aid will be placed over the site. Emergency treatment is accessible on campus for any severe complications from blood draw.

Protection from Risk from Information on CMV Serology and Infection:

Information about CMV infection will not be shared with individual subjects or their physicians. In addition to the importance of maintaining the “firewall” between our clinical and genomic studies, there is at this time no evidence that a positive CMV serology should result in any specific course of action on the part of the patient or his/her physician. As a result, a decision to share such information would only result in unnecessary anxiety and confusion.

Protection against Risk of Vaccination with Prevnar 13:

A detailed medical history questionnaire will be completed by the participant and reviewed by a qualified member of the study team to identify contraindications to vaccination and to determine study eligibility. For eligible participants, assigned vaccine will be administered by a Registered Nurse as a single dose, given intramuscularly in the deltoid. Participants will be required to remain on site for 30 minutes after vaccine administration so that they can be monitored for adverse events.

Protection against Risk of Vaccination with Pneumovax 23:

In addition to protections listed under vaccination with Prevnar 13, participants will be asked about recent vaccination with Zostavax for shingles within the prior 28 days from date of planned vaccination or if they are planning to receive Zostavax in the 28 days following. In order to optimize response to all vaccines, study entry may be delayed to allow 28 days between vaccine administrations. If study entry is delayed, eligibility criteria will be reviewed and confirmed prior to randomization.

Protection against Risk from optional second vaccination one to two years after initial vaccine (Visit 7):

Participants that opt into a second vaccination with the vaccine not assigned at baseline will receive the benefits of two vaccinations for pneumococcal infection at no cost to them. Both vaccines are FDA approved for healthy adults 65 and older and children and adults 2 to 64 years of age with certain chronic health conditions. Vaccinations are given at the dose and via the route (intramuscular injection) as approved. Medical history will be reviewed and eligibility re-confirmed before the second vaccine is administered by an RN at optional Visit 7.

7.3 Adverse Events and Serious Adverse Events

An **adverse event (AE)** is defined as any unfavorable and unintended diagnosis, symptom, sign, syndrome or disease which either occurs during the study, having been absent at baseline, or if present at baseline, appears to worsen. Adverse events will be collected and recorded at each visit regardless of their relationship to the study intervention or to study participation.

A **serious adverse event (SAE)** is defined as any untoward medical occurrence that results in death, is life threatening, requires inpatient hospitalization or prolongation of existing hospitalization, results in persistent or significant disability/incapacity, or is a congenital anomaly.

7.4 Reporting Procedures

The Clinical Principal Investigator will review all AEs and SAEs to assess causality. The IRB requires reporting of unexpected adverse events that may represent an unanticipated problem involving risks to subjects or others (UPIRSO). Such events are to be reported to UConn Health IRB using the Problem Report Form within the IRIS electronic IRB submission system.

7.5 Treatment for Adverse Events

UConn Health does not provide insurance coverage to compensate for injuries incurred during research. UConn Health does not offer free care. However, treatment for a research related injury can be obtained at UConn Health for the usual fee. Medical care at UConn Health will be available to study participants for treatment of an adverse event at normal cost.

7.6 Data and Safety Monitoring

Data and Safety Monitoring Plan

The Data & Safety Monitoring Plan for this study describes the components of the study that will be monitored by the PI, study coordinator and data manager once annually. Recruitment, drop outs, adverse events, unanticipated problems, data integrity and confidentiality, participant privacy and the general conduct of the study will be reviewed. Minutes of the annual DSMP review will be kept in the regulatory binder and provided to IRB at study continuation. The vaccines given in this study are given at the dose, via the route and in the population for which they are approved by FDA, and study samples are limited to peripheral blood draws in healthy older adults, thus this study poses minimal risk to research subjects. As a result, a Data Safety Monitoring Board (DSMB) is not indicated. Nevertheless, robust procedures are in place to ensure confidentiality of research data.

Procedures in place to ensure confidentiality of research data are as follows:

1. Only authorized individuals have access to any data, used or stored (via electronic format or as hard copy records). Only designated research staff and investigators will be granted access.

2. Logon IDs and passwords for access to the UConn Center on Aging shared network drive and the University's online resources are initially assigned by the Information Technology Department (IT).
3. All data (clinical, recruitment and schedule-based) are stored in password-protected databases on the secured network drive. Only approved personnel have access to these databases and passwords.
4. All data collected on data forms are stored in locked drawers located in the Center on Aging research facility for scanning and verification purposes. Files are stored in locked cabinets in rooms that are locked when not in use. All data are backed up on the shared network drive for UCHC.

8 INTEGRATIVE DATA ANALYSIS

8.1 Statistical Methods

The breadth and magnitude of IgG titers will be analyzed individually and together using best-response and multivariate U-statistic approaches [4, 97]. Differences among groups (e.g., responder status) and/or time of immunological variables (e.g., flow, RNAseq) will be assessed using generalized linear mixed-model analyses with appropriate distributional assumptions (e.g., normal, negative binomial) and link functions (e.g., identity, log). Propensity scores [98] will be adjusted for possible confounds such as gender, age, race and ethnicity, while the Bonferroni correction or Benjamini and Hochberg false discovery rate (FDR) will account for multiple testing [99]. Correlation of clinical and immunological variables will be conducted using the Pearson or Spearman Correlation Coefficient depending on whether or not the assumptions of linearity and homoscedasticity are met. For class prediction, a variety of methods including k-nearest neighbors, radial basis machine, random forests, boosted trees and support vector machines will be employed and validated using leave-one-out cross-validation. Unsupervised analysis of high dimensional data will be conducted using heatmaps, hierarchical cluster analysis and principal component analysis. Lastly, attrition and missing data are issues in longitudinal [100] and elderly studies [101]. "Missingness" will be characterized and multiple imputation applied when appropriate [102-104]. Drs. [name] (JAX) and [name] (SIDRA) will assist with statistics and bioinformatics as needed.

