Antibody responses: We will analyze the breadth and magnitude of antibody responses by assessing PPSV23/PCV13 serotype-specific IgG titers at day 0 and 28, as recommended by the World Health Organization, and using the Opsonophagocytic assay. This assay (serotypes 4, 6B, 14 and 23F) will be performed using serotype-specific *S.pneumoniae* incubated with serial-diluted heat-inactivated sera [3]. Newborn rabbit serum is added as a source of complement and differentiated HL-60 cells are added. Sera are tested in duplicate and results obtained using the Opsotiter 1 software. We will use U-scores to rank antibody response by titer, affinity and number of serotypes (as done for antigen-specific T cells in response to DC vaccines [4-6]. Our collaborator, [name], will assess serotype-specific anti-polysaccharide responses. His lab will also measure antibody avidity and opsonizing capacity as described [7].

CMV status. Influenza vaccine studies in the elderly have revealed a critical role for CMV status [8]. In a single study, CMV status did not appear to influence antibody responses to PPSV23 vaccine in older adults, yet its role in other aspects of immune responses or in baseline pre-vaccination status cannot be ruled out[9]. As a result, we will obtain CMV status using antibody titers and PCR-based technologies [10], and will include this variable in our analytic plan.

Analytical Approaches:

1. *Multicolor flow cytometry*: 0.5 ml of blood will be used to determine the profile of circulating immune cells. We designed five multi-color monoclonal antibody cocktails that will permit us to establish the detailed phenotype of T-cell subsets, monocytes, DCs and B-cell subsets. We included a set of antibodies to identify NKT cells, as these cells have been reported to contribute to responses to PPSV23 vaccination [11].

2. *Cryopreservation of isolated PBMCs and sorting of purified populations*: We have validated monoclonal antibody cocktails that permit us to sort T-cell subsets, monocytes, DCs and B cells for cryopreservation (**Table 1**). PBMCs will be frozen in 4–5 aliquots (recovering on average 20×10^6 cells); 1–2 will be used for ATAC-seq and 2–3 for functional studies. After thawing we will sort monocytes, CD1cDCs, CD45RO+CD4+ T cells, and B cells for ATAC-seq and RNA-seq. We aim to collect 15,000–25,000 of each type of cells.

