To investigate our hypothesis we will apply RNA-seq, rather than DNA microarrays, to generate transcriptional profiles, as this will enable quantitative assessment of both coding RNAs and ncRNAs. We will also use ATAC-seq to resolve the epigenetic landscape of immune cells in healthy elderly in the context of vaccine responses.

Approach:

1. *Blood transcriptomics by RNA-seq:* We will carry out RNA-seq of whole blood samples at baseline, day 1 and day 10. Samples collected from days 28 and 60 will be kept frozen for future studies. RNA-seq on purified cell subsets will be performed using purified cells from the five lowest and five highest responders for each vaccine. Sequencing will be performed at JAX-GM with an Illumina HiSeq2500.
2. *Blood epigenomics analysis by ATAC-seq:* We will analyze PBMCs, CD4+ T cells, monocytes, CD1cDCs and B cells (25×10^3 cells per assay). We are also developing assays with lower cell numbers to address the scarcity of some populations, and are encouraged by reports of single cell ATAC-seq [17]. We will generate a database describing the DNA accessibility landscape of major immune-cell subsets from elderly individuals at steady state. The data will also include the DNA accessibility landscape of monocytes, T and B cells analyzed at different time points following vaccination with the two pneumococcal vaccines. For these in-depth studies, we will select the five highest and five lowest responders for each vaccine.

Correlative analysis: We will correlate the increased levels of day 28 anti-pneumococcal antibodies as defined in Aim 1 with all the parameters collected in this aim. Parameters include: 1) cellular composition at baseline, day 1 and day 10 post-vaccination; 2) transcriptome analysis on blood and purified immune cell subsets at baseline, day 1 and day 10; 3) ATAC-seq data on PBMCs and purified cell subsets at the different time points and 4) pneumococcal colonization at baseline and at day 28. A detailed description of the statistical approaches is given below (see Integrative Data Analysis section).

1.3 Specific Aim 3

To examine the functional status of immune cells in the elderly stratified according to their pneumococcal vaccine responder status.

Hypothesis: We hypothesize that lack of *in vivo* response to PPSV23 and PCV13 depends on alterations to APCs, Tfh cells or B cells.

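### The mixed models in Section 8.1 name responder groups but no continuous antibody term, so for assays run on everyone the adjusted longitudinal test of antibody response exists only in categorised form

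*Combined protocol and SAP*

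**What the plan says.** Section 8.1 gives one model-based analysis of the immune variables: "Differences among groups (e.g., responder status) and/or time of immunological variables (e.g., flow, RNAseq) will be assessed using generalized linear mixed-model analyses". The next sentence adds propensity-score adjustment for demographic confounders (gender, age, race, ethnicity) and multiplicity control. Section 1.1 adds that CMV status will enter the analysis.

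A graded response measure exists. Section 1.1 states: "We will use U-scores to rank antibody response by titer, affinity and number of serotypes".

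Two assays are planned without a responder restriction. Table 1 schedules flow cytometry at all six visits, and Section 1.2 says of whole blood: "We will carry out RNA-seq of whole blood samples at baseline, day 1 and day 10". The restriction to "the five lowest and five highest responders for each vaccine" is attached in Section 1.2 to RNA-seq on purified subsets, with the same selection for the in-depth ATAC-seq work. Section 1.3 uses groups of five for functional studies.

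Correlations are planned as well. Section 1.2: "We will correlate the increased levels of day 28 anti-pneumococcal antibodies as defined in Aim 1 with all the parameters collected in this aim". The listed parameters include "cellular composition at baseline, day 1 and day 10 post-vaccination" and "transcriptome analysis on blood and purified immune cell subsets at baseline, day 1 and day 10". Section 1.1 relates day 28 antibody to T-cell activation at day 10 and APC activation at day 1. Section 8.1 names the statistic: "Correlation of clinical and immunological variables will be conducted using the Pearson or Spearman Correlation Coefficient".

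**The concern.** Limiting purified-cell assays to extreme responders saves cost and cells. That reason does not apply to an assay already run on all participants. For those assays, replacing a ranked score by a high/low label drops either the middle participants or the ordering within each half, and the result then depends on where the cut falls. No cut-off for the full cohort is stated, so one would have to be chosen later, possibly with the data in view.

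A bivariate coefficient cannot fill the gap. It cannot use repeated visits jointly, test whether the antibody association changes over time, or carry the demographic and CMV adjustment. The plan also does not say which analysis leads if the correlation and the group model disagree. With 40 people and multiplicity control, the adjusted test should not be the less efficient of the two.

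**Working it through.** **The plan's own figure.** Section 8.2 states more than 90% power with 20 per cohort for at least 6,000 genes: two-sample t-test, SD 0.7 on the log2 scale, FDR 1%, 37,649 genes. I take the 2-fold difference (1 log2 unit) as the effect, which is an assumption.

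- Per-gene alpha = 0.9 × 6,000 × 0.01 / [(37,649 − 6,000) × 0.99] = 0.00172, critical z = 3.13.
- Signal = 1 / (0.7 × √(2/20)) = 4.52.
- Normal-approximation power = Φ(4.52 − 3.13) ≈ 92%, consistent with the stated figure. The exact t gives about 86%.

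This is a two-group calculation. The plan gives no figure for an antibody-score association, so it does not settle the present point.

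**Which analysis can do what, from the text:**

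| Feature | Mixed model (8.1) | Correlation (1.1, 1.2, 8.1) |
|---|---|---|
| Keeps the ordering of antibody response | Not if responder status is the term | Yes |
| Repeated visits, score-by-time | Could, but no score term is named | No |
| Covariates | Yes | No |

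No planned analysis does all three.

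**Information kept by a group contrast.** Assume a normal score and a linear relation. With a fraction q in each tail and m = φ(z)/q the mean score in that tail, the contrast keeps 2qm² of the information in the continuous slope.

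- Top against bottom quarter: q = 0.25, z = 0.674, m = 1.271; 2 × 0.25 × 1.271² = 0.81.
- Median split: q = 0.5, z = 0, m = 0.798; 2 × 0.5 × 0.798² = 0.64.
- Simulated at n = 20 (one vaccine): 0.80 for 5 v 5 and 0.64 for 10 v 10.
- Uneven splits of 20: 0.62 for 8/12 and 0.57 for 6/14.

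If the relation is instead linear in rank (ranks 1 to 20, variance (20² − 1)/12 = 33.25), the contrast keeps more:

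- 5 v 5: 7.5² × 0.5 / 33.25 = 0.85.
- 10 v 10: 5² / 33.25 = 0.75.

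**Power illustration** (n = 20, two-sided 5%, 40,000 simulated samples; the correlations are assumed):

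| True correlation | Continuous score | 5 v 5 | 10 v 10 |
|---|---|---|---|
| 0.5 | 64% | 46% | 42% |
| 0.6 | 84% | 65% | 60% |

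A simple rank score gives 80% at correlation 0.6. The continuous column is an unadjusted slope test, which is the same test as the Pearson correlation already planned. The table therefore shows the cost of categorising; it does not show the gain of the revised plan over the present one.

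**The case against.** The strongest reply is that the ordering is already used. The planned correlations cover cell composition and the blood transcriptome, and nothing in the text limits them to extreme responders. That is right. A reader might infer that the plan as a whole loses 19% to 36% of its information; the documents do not support this.

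A reader might also infer that the middle ten people per vaccine are dropped from flow and whole-blood analyses. That is not specified. The five-and-five rule belongs to purified-subset, in-depth and functional work. Only the opening of Section 1, which says broadly that phenotype and transcriptome work is done on selected responder extremes, points more widely. A median split appears nowhere in the documents.

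Next, responder status is only an example in Section 8.1. Vaccine arm is also a group, and effects of time need no responder split. This stands, and it is why the figures are conditional.

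Finally, Aim 3 concerns failure to respond. A responder contrast in whole blood lines up with the five-and-five assays, and if non-response is a threshold phenomenon a linear score need not be more efficient. This also stands, and it is a reason to keep the groups for those assays and for display.

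What the reply leaves open is the adjusted longitudinal test, which has no graded antibody term, together with the missing full-cohort cut-off and the missing order of precedence.

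**Conclusion.** The point holds in a limited form. The only adjusted longitudinal model is described for groups and names no continuous antibody term, even for assays run on everyone, while the analyses that keep the ordering are unadjusted and have no time structure.

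If responder status is the term used, the group test keeps about 81% (extreme quarters) or 64% (median split) of the information in a continuous score. These values rest on assumed cuts, a normal score and a linear relation. They are not bounds: uneven splits keep less, and a relation linear in rank keeps more. They do not measure a loss for the plan overall. This is a cheap improvement of low severity; it does not invalidate the planned analysis.

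**What to change.** In Section 8.1, state that for assays run on all participants (flow cytometry, and whole-blood RNA-seq at baseline, day 1 and day 10):

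- the mixed model includes the antibody score, continuous or ranked within vaccine, with vaccine, time, score-by-time and the planned covariates including CMV status;
- this is the lead antibody-association analysis, and the Pearson or Spearman correlations are supportive;
- high/low responder groups are kept for the five-and-five assays and for plots.

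The cost is analysis-plan wording only, with no new samples or visits. The small downside is that a monotone relation is assumed, which a plot of each reported variable against the score can check, and that a threshold-type non-response would be fitted less directly.
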